The aim of this study is to test whether and to what degree a community-based karate class tailored for individuals with early- to middle-stage Parkinson's Disease (PD) 1) is feasible; and 2) improves objective mobility and balance, 3) improves patient-reported outcomes in mobility, balance, camaraderie, and overall wellbeing compared with individuals given a standard exercise prescription for PD. The benefits of exercise for general health and wellbeing in older adults are well-established. Balance exercises such as tai chi and yoga, along with resistance training, can improve or maintain physical function in older adults and enhance muscle strength. Furthermore, aerobic activity is critical for maintaining and improving cardiovascular and functional health. Non-contact boxing has seen a surge in popularity among individuals with PD, with components of both aerobic and balance exercise. While participants anecdotally note improvements in stress and physical function, this has only been minimally studied. However, drawing on the enthusiasm for boxing, literature surrounding aerobic and balance exercise in PD, and the combined aerobic, balance, and mindfulness practices that comprise karate, we hypothesized that participation in structured karate programs may offer similar or greater benefits than any of the individual components above. In particular, the aerobic, resistance, and balance aspects of karate may be beneficial for physical and cognitive wellbeing, and the mindfulness exercise may improve overall wellbeing. Therefore, we conducted a pilot, 10 week-long study of a structured karate exercise program for people with early to middle PD during the summer and early fall of 2018. In this single-arm pilot (no control participants), we assessed mobility, gait, balance, falls, attention, quality of life, patient-reported global impression of change, and mood before and after the 10 weeks of karate. Among 15 participants completing 10 weeks of twice-weekly classes, our pilot data highlighted our feasibility: adherence was high (mean attendance 87% of 20 classes), 100% of participants indicated interest in continuing karate classes, and 100% would recommend the program to other individuals with PD, respectively. Additionally, participants experienced a statistically and clinically significant improvement in quality of life, as measured by the Parkinson's Disease Questionnaire-Short Form (PDQ-8), with mean scores improving from 25.3 to 19.3 ($p < 0.01$), significant improvements in measures of working memory and executive function, and a trend toward improvement in the Timed Up and Go mobility measure (9.6 seconds pre-intervention to 9.0 seconds post-intervention, $p = 0.12$). Further data analysis—including qualitative analysis—is underway.

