Our sample size calculation (see table below) is based on the results from the pilot study with the primary outcome being change in TUG. We powered our original study based on existing literature, in which the mean TUG score for individuals with PD is 14.8 seconds with standard deviation of 5.8 seconds, and minimum clinically important difference values for the TUG ranged from 2 seconds to 5 seconds in various studies.^{1,17} However, our pilot cohort had a pre-intervention baseline mean TUG of 9.6 seconds, standard deviation of 2.1. As per the tables below, if our new cohort has a similar baseline mean TUG, we would need 12 individuals in each arm to detect a difference of 2 seconds with 90% power, however this may not be plausible (i.e., 9 seconds may be close to the limit of how quickly anyone can complete the TUG task). If, however, participants have a more modest baseline to start, which may be expected when recruiting more broadly than at a tertiary referral center, we yield the second half of the table below. Here, we are extrapolating a baseline mean TUG of 12.5 with SD 4.0 (between our pilot data and the existing literature); with 19 individuals per arm, we would be 90% powered to detect a 3s difference between pre- and post-intervention TUG.

If we assume up to 25% attrition in this group of older adults with a chronic neurodegenerative disease, particularly in a longitudinal study over six months, we need to enroll 52 individuals (26 per arm) to yield a total of 40 completing the study.

Baseline mean TUG	Baseline SD TUG	Minimum clinically Important difference	Power	Sample size per arm
9.6	2.1	2s	.9	12
			.8	9
9.6	2.1	3s	.9	6
			.8	4
9.6	2.1	4s	.9	3
			.8	3
9.6	2.1	5s	.9	2
			.8	2
12.5	4.0	2s	.9	43
			.8	32

12.5	4.0	3s	.9	19
			.8	14
12.5	4.0	4s	.9	11
			.8	8
12.5	4.0	5s	.9	7
			.8	6

II.b. Gender of Subjects

There will be no exclusion of subjects based on gender.

II.c. Age of Subjects

Subjects will be 30-90 years of age.

II.d. Racial and Ethnic Origin

There will be no exclusion of subjects based on racial or ethnic characteristics. However, subjects must be fluent in English to participate in the karate classes, as that is the language of instruction, and due to the general lack of appropriately translated neurological and neuropsychological assessments and appropriate normative comparison samples. These factors are critical for accurate administration, scoring, and interpretation of neurological and neuropsychological test data.

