Data will be exported from REDCap in de-identified format for statistical analysis, with all PHI stripped from the dataset prior to analysis by statisticians. We will summarize categorical variables by frequencies and percentages and will assess continuous variables for normality, summarized by mean/standard deviation, or median/interquartile range. We will report the basic descriptive statistics of the cohort, including baseline demographics, TUG, MDS-UPDRS, HADS, PDQ-8, IPAQ, SDMT, MoCa, and DST. We will report on attendance, defined as the percentage of classes attended, in each arm once active. We will analyze the change in TUG, MDS-UPDRS, HADS, PDQ-8, IPAQ, SDMT, DST, MoCa, and PAGEQ respectively, from baseline to six months, comparing Arm 1 and 2 (active vs. control), and again at twelve months to determine whether longer participation yields additional benefits, using paired *t*-tests or nonparametric Wilcoxon sign rank tests, as appropriate. We will report on the percentage of subjects endorsing each of the 7 PGIC response options at six and twelve months, between Arms, respectively. We will report the descriptive statistics concerning whether subjects’ individual predefined goal for the class was achieved (binary outcome), and will present de-identified qualitative comments noted in the feedback at the study visit focus groups. We will report descriptive statistics on continued interest and likelihood of recommending the program to someone else with PD. We will analyze descriptive statistics on continued involvement in karate/martial arts, and will again report the percentage of subjects endorsing each PGIC response option.

The qualitative data from the study visit focus groups will be audio-recorded and transcribed, with all identifying information stripped from the transcripts. Once transcribed, the audio recordings will be destroyed. The qualitative data will be analyzed using a grounded theory approach to identify pertinent themes, with data stored as password-protected files behind the Rush firewall, accessible only to study staff.

All video footage will be the sole property of the PI. Videos will have identifying information (i.e. image of patient’s face, first name). Video files will be stored and password-protected behind the Rush and the Columbia firewalls. The video along with the data collected from the focus groups and karate classes may be used as part of the dissemination of the study results and for educational purposes.

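### The six-month arm comparison uses raw change with no adjustment for the baseline value, which costs some precision and lets a share of any chance baseline difference into the result

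*Combined protocol and SAP*

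**What the plan says.** Section II.a bases the sample size on change in TUG, described as "based on the results from the pilot study with the primary outcome being change in TUG". Section III.b then states: "We will analyze the change in TUG, MDS-UPDRS, HADS, PDQ-8, IPAQ, SDMT, DST, MoCa, and PAGEQ respectively, from baseline to six months". The contrast is given as "comparing Arm 1 and 2 (active vs. control), and again at twelve months", and the tests are paired t-tests or "nonparametric Wilcoxon sign rank tests, as appropriate".

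Baseline values enter in two ways. They are subtracted to form the change, and they are summarised: "We will report the basic descriptive statistics of the cohort, including baseline demographics, TUG", with the other scales following. No section names a regression model, an analysis of covariance or any covariate.

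Section I.c randomises 1:1 within each dojo. Nothing in the design balances baseline TUG between arms.

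Section II.a also raises a possible floor on the TUG: "9 seconds may be close to the limit of how quickly anyone can complete the TUG task".

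**The concern.** Subtracting baseline amounts to assuming that six-month TUG rises one second for every second of baseline TUG. If the true slope is below 1, the change score over-corrects. The arm that starts slower by chance then appears to gain more, and part of the variance that baseline could explain stays in the error term. The floor remark in section II.a is a reason to expect such a slope in this cohort.

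The trial is small, with 40 completers expected in total, so chance baseline differences will not be negligible and precision is worth keeping. The point is separate from the choice of a paired test. Replacing the paired test with a two-sample test of change would still leave the baseline unused as a covariate.

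**Working it through.** **Inputs**
- Section II.a: baseline SD 2.1 s (pilot) with a 2 s difference, or SD 4.0 s (extrapolated) with a 3 s difference; 40 completers, taken as 20 per arm.
- Opening section on aims: pilot TUG fell from 9.6 to 9.0 s, p = 0.12, n = 15.
- Not in the documents: rho, and the SD at six months. I assume equal SDs at both visits and show a range for rho.

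**The plan's own figure.** With two-sided alpha 0.05 (not stated, but it fits), n = (SD × (z0.975 + z0.90)/difference)² = (4.0 × (1.960 + 1.282)/3)² = 18.7, so 19. The same formula, with the relevant z for power, gives all 16 table rows. Then 19/0.75 = 25.3, so 26 per arm. This is a single-group before–after formula with the baseline SD used as the SD of change. Under equal SDs, Var(change) = 2·SD²·(1 − rho), which equals SD² only when rho = 0.5. Read this way, the table is consistent with rho = 0.5.

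**rho implied by the pilot.** If the p-value came from a paired t-test, t on 14 df is 1.656. SD of change = 0.6 × √15/1.656 = 1.40 s. Then rho = 1 − 1.40²/(2 × 2.1²) = 0.78. Because the means are rounded, a true mean change of 0.5 to 0.7 s would give rho of about 0.84 to 0.70.

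**Formulas**
- Variance ratio, adjusted to change score: SD²(1 − rho²)/[2·SD²(1 − rho)] = (1 + rho)/2.
- Standard error of the baseline difference: SD × √(2/20) = 0.66 s (SD 2.1) or 1.26 s (SD 4.0).
- Shift in the change contrast for a baseline difference D: (1 − rho) × D, in favour of the arm that starts slower.

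**Results.** The shift is for a one-standard-error baseline difference. Power is for a two-arm comparison, 3 s, SD 4.0, 20 per arm, using large-sample variances.

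| rho | Variance ratio, large sample | Simulated, 20 per arm | Shift, SD 2.1 | Shift, SD 4.0 | Power, change vs adjusted |
|---|---|---|---|---|---|
| 0.5 | 0.75 | 0.77 | 0.33 s | 0.63 s | 66% vs 78% |
| 0.7 | 0.85 | 0.88 | 0.20 s | 0.38 s | 86% vs 91% |
| 0.78 | 0.89 | 0.92 | 0.15 s | 0.28 s | 95% vs 97% |
| 0.9 | 0.95 | 0.97 | 0.07 s | 0.13 s | over 99% for both |

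Against each scenario's own target, for rho 0.78 to 0.5, the shifts are 0.15/2 = 7% to 0.33/2 = 17% (SD 2.1), and 0.28/3 = 9% to 0.63/3 = 21% (SD 4.0).

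**Unequal SDs.** Keep the pilot SD of change at 1.40 s and baseline SD at 2.1 s. If the later SD were 15% smaller (1.785 s), the covariance is (4.41 + 3.19 − 1.97)/2 = 2.81 and the slope is 2.81/4.41 = 0.64. Then 36% of an imbalance carries over and the variance ratio is 0.71. If the later SD were 15% larger, 6% carries over and the ratio is 0.99. The 15% is my assumption. A floor would point to the first case.

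**The case against.** The main objection is that the gain is modest and the defect secondary. At the pilot-implied rho, the large-sample saving of 11% falls to about 8% once the cost of estimating the slope with 20 per arm is counted. It becomes material for power only if rho is near 0.5. The named tests are also not two-sample tests, so that sentence has to be rewritten anyway. All of this stands. It argues for making the adjustment part of that rewrite, not for leaving it out. Rho over six months could also be lower than over the pilot's 10 weeks.

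A reader might infer several stronger things that the documents do not support:
- *That a chance baseline difference passes into the result in full.* A difference above 0.6 s, the size of the pilot effect, has probability 37% (SD 2.1) or 64% (SD 4.0) with 20 per arm. But the change score already subtracts baseline. At rho 0.78 only about 0.13 s of a 0.6 s imbalance remains. A carried shift above 0.6 s then has probability under 0.1% (SD 2.1) or 3% (SD 4.0).
- *That shifts of 0.28–0.63 s rival the 0.6 s pilot effect.* Those shifts belong to the SD 4.0 scenario, whose target is 3 s. The pilot effect belongs to the SD 2.1 cohort.
- *That the estimate is biased.* Allocation is random, so it is unbiased on average. The shift is conditional on the imbalance that occurs, and the standard error already reflects it.
- *That every outcome is a change score, or that baseline is only described.* PGIC, attendance and goal achievement are reported differently, and baseline is used to form the change.
- *That fast walkers cannot improve.* Section II.a says only that there may be a limit.
- *That the test is chosen after a normality check.* Section III.b links normality to the summary statistics. For the tests it leaves the choice open without giving a rule.

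It is also fair to say that a common-slope model does not describe a karate effect that varies with baseline. It estimates an average adjusted difference and should be reported as such.

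**Conclusion.** The point holds as a matter of efficiency and conditional bias, not of validity. The plan compares raw change between arms and does not adjust for a baseline value that it already collects. The variance saving is about 8–11% at rho 0.78, and 25% to 5% (large-sample) over rho 0.5 to 0.9. On the same 40 completers, 8–11% is worth roughly 3 to 4 participants.

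These sizes rest on an assumed rho, equal SDs at the two visits, rounded 10-week pilot figures and an assumed paired t-test in the pilot. The direction is firmer than the size: in large samples the adjusted comparison is never less precise than the change score, and the simulations at 20 per arm still show a gain at every rho tried. The change should be made, together with the correction of the test.

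**What to change.** In section III.b, specify the primary six-month analysis as a linear model of month-6 TUG on arm, baseline TUG and dojo (the randomisation stratum), reporting the adjusted arm difference with its 95% CI. Use the same model for each other listed scale that has a baseline value. PAGEQ is not among the baseline assessments in section I.c or under the pre-intervention visit, so neither its change nor its adjustment can be computed as written.

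This model replaces the paired and signed-rank tests for the between-arm comparison and removes the open choice between them. Pre-specify a bootstrap or permutation interval from the same model as a sensitivity analysis, to be run whatever the residuals look like.

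The cost is wording only, with no new data or visits. With five dojos the model has 1 intercept + 1 arm + 1 baseline + 4 dojo = 7 parameters, leaving 40 − 7 = 33 residual degrees of freedom.

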
Based on these promising results from the pilot, we are therefore proposing the next step in this line of research, namely, a randomized, controlled trial of a structured karate intervention for individuals with PD. Individuals will receive a one-time, in-person training in best practices for exercise in PD. Due to both the capacity of the karate classes and the scientific approach to detecting changes in PD, subjects will be randomly assigned into either **Arm 1**: immediate participation in the karate class or **Arm 2**: participation in usual exercise for six months followed by karate classes for six months. For participants in **Arm 1**, following the first six months of classes, subjects may choose to continue their participation in karate and in the study, though this will require paying membership fees at the *dojo* (karate studio). For participants in **Arm 2**, following the first six months of usual exercise, participants will then begin 6 months of twice-weekly classes. We will conduct in-person assessments of motor function, attention, and cognition at baseline, six months, and twelve months. We will conduct online assessments of adherence to exercise program, quality of life, anxiety, depression, global impression of change, and group cohesion via bimonthly online surveys. We will assess feasibility with measurement of attendance at each class, and sustainability with the rate of attendance among the participants beyond their first six months of classes.

We hypothesize: 1) Subjects will show improved mobility after 6-months of twice weekly karate classes, as measured by change in Timed Up & Go (TUG)¹ and MDS-UPDRS motor subscore; 2) The majority of subjects will report a positive change from baseline in their overall wellbeing, as measured by a response of “very much improved”, “much improved” or “minimally improved” on the Patient Global Impression of Change Scale (PGIC)² following 6 months of classes; 3) Feasibility will be high, as measured by $\geq 75\%$ attendance rate and a response of “yes” to either “Would you recommend this program to someone else with PD?” or “If available, would you continue to participate in this or a similar karate class?”

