This is a randomized, single-blinded, crossover-controlled, one-year study of non-contact karate for early- to middle-stage PD. The karate classes are developed for and will include only people with PD. Eligible subjects will attend a baseline study visit at Rush University Medical Center. At that time, the study logistics will be reviewed, informed consent process will occur, and each subject will complete brief, individual pre-intervention assessments including a demographic and medical history questionnaire, followed by assessments of overall mobility, gait, and balance (instrumented Timed up and Go, I-TUG; instrumented 2-minute walk, I-WALK, and instrumented sway test, I-SWAY), PD-specific clinical characteristics (Movement Disorders Society Unified Parkinson's Disease Rating Scale, MDS-UPDRS), overall cognition (Montreal Cognitive Assessment, MoCA), executive function and attention (digit span test, DST, and symbol digit modality test, SDMT), anxiety and depression (Hospital Anxiety and Depression Scale, HADS), physical activity (International Physical Activity Questionnaire, IPAQ) and quality of life (PDQ-8). Instrumented gait analysis will be performed to gather more detailed data on stride length and velocity, number of steps to turn, turn duration, and postural sway.¹⁶

During recruitment, and confirmed by the Research Coordinator during the baseline visit, each subject will be asked to identify their preference for karate studio (dojo) location: Roscoe Village, Evanston, Glenview, Park Ridge, or Wilmette.

Once all subjects have completed the objective and subjective baseline assessments, the baseline visit will continue with a one-time, in-person, group training highlighting current research on the benefits of exercise for PD. This training will be delivered by the study team in collaboration with an experienced physical therapist familiar with evidence-based recommendations for safe and effective exercise programs for individuals with early to middle stage PD. Participants will leave the training with printed, publicly available materials on exercise for PD as references.

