After the training, eligible subjects will be grouped by dojo preference, and randomized 1:1 within each dojo into **Arm 1**: immediate participation in six months of twice-weekly karate classes, or **Arm 2**: usual exercise for six months. After six months, Arm 1 participants may opt to pay for dojo membership and continue classes, and Arm 2 participants will crossover and begin six months of twice-weekly karate classes. Only the Research Coordinator will know which subjects belong to Arm 1 and Arm 2, and she/he will deliver all study-related communication to the subjects.

The karate classes have been specifically designed for individuals with early- to middle-stage PD, focused on incorporating upper and lower limb movements in multiple directions, increasing awareness throughout the body, shifting body weight and rotation, relaxation of the muscles, improving reaction time, using complex repetitive actions to improve coordination, footwork training and centered weight shifts to help with fall prevention, and striking shields for self-defense and stress relief. The PI and study team will provide instruction on PD to all instructors prior to study launch, and will be available and responsive to any questions or concerns throughout the course of the study. The structure of the 6-

month curriculum will be identical at each of the five dojo locations. If a subject misses a class, they may choose to make up a class at one of the other dojo locations.

Every two months, subjects in both Arms will receive an online link to report their attendance at classes, indicate whether their PD medication regimen has changed (as a potential confounder), and complete the IPAQ, HADS, and PDQ-8. In addition, the survey will contain the Physical Activity Group Environment Questionnaire (PAGEQ) to measure camaraderie, and Patient Global Impression of Change (PGIC) for the subject's global impression of change. The online survey will be delivered through a secure online database called Research Electronic Data Capture (REDCap). The purpose of the online surveys is to track adherence to karate classes, adherence to other walking/moderate/vigorous activity, quality of life, anxiety, depression, global impression of change, and group cohesion.

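### The six-month comparison of karate with usual exercise is given only paired tests, which cannot compare two independent arms, and the sample-size table is not for that comparison either

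*Combined protocol and SAP*

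**What the plan says.** The opening section sets the efficacy aims as improvement "compared with individuals given a standard exercise prescription for PD". Section I.c (Study Design) calls the trial randomised and crossover-controlled, with participants "randomized 1:1 within each dojo" to immediate karate (Arm 1) or six months of usual exercise followed by karate (Arm 2).

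Section III.b (Data Analysis and Data Monitoring) will analyse change in TUG, MDS-UPDRS, HADS, PDQ-8, IPAQ, SDMT, DST, MoCA and PAGEQ "from baseline to six months, comparing Arm 1 and 2 (active vs. control". A second analysis of the same measures is then planned for the end of the study: "and again at twelve months to determine whether longer participation yields additional benefits". For both analyses the plan gives one choice of method: "using paired *t*-tests or nonparametric Wilcoxon sign rank tests, as appropriate". These are the only inferential tests named. PGIC, attendance and the feasibility questions are reported descriptively.

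Hypothesis 1 in the opening section is worded within person: "Subjects will show improved mobility after 6-months of twice weekly karate classes".

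Section II.a (Number of Subjects) takes change in TUG as the primary outcome. It tabulates sizes per arm from a baseline SD, and arrives at 19 per arm for 90% power to detect 3 s with SD 4.0 s, the effect being described as a pre-to-post difference.

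**The concern.** A paired t-test or signed-rank test needs observations linked in pairs. Nothing links an Arm 1 participant to an Arm 2 participant, so neither test can address the stated arm comparison. The qualifier about appropriateness only chooses between a parametric and a nonparametric paired procedure.

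This matters because some change is likely to be shared. Both arms receive the same exercise training at baseline and repeat the same tests, and the disease is progressive. A within-arm test credits shared improvement to karate, and shared decline can hide a real benefit. The control arm protects against both errors only if the arms are compared. Without that comparison the trial repeats the main limitation of the single-arm pilot it was designed to follow.

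The sample-size table raises the same question: is its 90% the power of an arm comparison or of a single-arm pre-post test?

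A smaller point in the same sentence of III.b is that change in PAGEQ is listed, although PAGEQ is not among the baseline assessments in I.c or III, nor in III.b's own list of baseline measures.

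**Working it through.** **1. Does the design supply pairs?** Only Arm 2 crosses over. Arm 1 has no assigned control period: "After six months, Arm 1 participants may opt to pay for dojo membership and continue classes". A paired contrast of karate with usual exercise therefore exists only in Arm 2, and always in the same order. The crossover label does not rescue the paired test for the six-month arm comparison.

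**2. Reproducing the table in II.a.** Alpha is not stated; two-sided 0.05 is assumed.

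One-sample formula: n = ceil(((1.960 + z_power) × SD / difference)²).

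- SD 4.0, 3 s, 90%: ((1.960 + 1.282) × 4.0 / 3)² = 18.68, so 19, as stated.
- SD 2.1, 2 s, 90%: 11.58, so 12, as stated.
- SD 4.0, 2 s, 90%: 42.03, so 43, as stated.

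The formula matches 16 of 16 rows. The two-sample formula on the same inputs doubles the unrounded value (2 × 18.68 = 37.36, so 38 instead of 19) and matches none. The figure of 38 is not the required size, because it treats 4.0 s as the SD of change, which is true only at a correlation of 0.5.

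**3. Power of the arm comparison.** Inputs: 3 s, 19 per arm, single-visit SD 4.0 s at both visits, two-sided 0.05, noncentral t. The baseline to six-month correlation r is an assumption, since the plan gives none. SD of change = 4.0 × √(2(1 − r)); ANCOVA residual SD = 4.0 × √(1 − r²).

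| r | SD of change | Power, two-sample test on change | ANCOVA SD | Power, ANCOVA |
|---|---|---|---|---|
| 0.50 | 4.00 | 61% | 3.46 | 74% |
| 0.70 | 3.10 | 83% | 2.86 | 88% |
| 0.78 | 2.65 | 92% | 2.50 | 95% |

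Reaching 90% with 19 per arm needs r of about 0.76 on change or 0.72 by ANCOVA.

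**4. What the pilot suggests about r.** The opening section gives a TUG change of 9.6 − 9.0 = 0.6 s, p = 0.12, n = 15. If that came from a paired t-test, t(14) = 1.656 and the SD of change is 0.6 / 1.656 × √15 = 1.40 s. Rounding (difference 0.5 to 0.7 s, p 0.115 to 0.125) gives 1.15 to 1.66 s. If both visit SDs are 2.1 s, r = 1 − 1.40² / (2 × 2.1²) = 0.78, range 0.69 to 0.85. This is over 10 weeks, not six months.

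**5. False credit from a within-arm test.** This is an illustration: 20 per arm, no karate effect, both arms improving equally. Chance that the Arm 1 paired t-test (two-sided 0.05) shows significant improvement:

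| SD of change (s) | Shared 0.6 s | Shared 0.3 s |
|---|---|---|
| 1.15 | 60% | 20% |
| 1.40 | 44% | 15% |
| 1.66 | 33% | 12% |
| 2.1 | 23% | 9% |
| 4.0 | 9% | 5% |

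The nominal rate in that direction is 2.5%. In simulation with the shared 0.6 s, a two-sample test on the same data held 4.9% to 5.1% two-sided.

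**The case against.** The best defence is that II.a describes a pre-to-post difference and Hypothesis 1 is within person, so paired tests and a one-sample formula fit what was hypothesised. That stands for Hypothesis 1, and paired tests should stay there. It does not supply a test for the arm comparison that III.b states and the aims require. Even for the within-person contrast, II.a uses a baseline SD where an SD of change is needed.

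On power, the objection has real weight. A two-sample calculation on change with r = 0.75 gives an SD of change of 4.0 × √0.5 = 2.83 s and the same 19 per arm. The pilot-implied 0.78 gives more than 90%. The plan states no correlation, however, and labels its SD as baseline, so the 90% cannot be read that way. The power point is a request for a stated assumption, not evidence that the trial is too small.

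The false-credit rates are also assumption-driven. No figure in the documents supports a shared six-month improvement of 0.6 s, which is the whole uncontrolled 10-week pilot change. The range matters more than any single entry, and the argument against the paired test does not depend on it.

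Finally, the defect leaves the feasibility and PGIC hypotheses untouched, since these rest on attendance and percentages.

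**Conclusion.** The concern holds and must be fixed. Followed as written, III.b cannot test the randomised six-month comparison it sets out, and no other section provides a test. This conclusion rests on the wording alone and is limited to the comparative efficacy aims.

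The table in II.a gives single-arm pre-post sizes, assuming two-sided 0.05. Its 90% is not the power of the arm comparison, which for 3 s and 19 per arm runs from 61% to 95% over correlations of 0.5 to 0.78 and the two candidate methods. The shortfall is conditional, and the planned 52 may be adequate for 3 s.

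**What to change.** 1. In III.b, name a between-arm method. Suggested text: *Six-month TUG, MDS-UPDRS, HADS, PDQ-8, IPAQ, SDMT, DST and MoCA will be compared between arms, by assigned arm, using ANCOVA adjusted for the baseline value; the difference and 95% CI will be reported.* A two-sample t-test on change would also cure the defect. Name a rank-sum test on change as the nonparametric alternative, because a t-test on change does not answer a failure of ANCOVA's normality or variance assumptions. Decide in advance whether to adjust for dojo (four dojo terms cost under 0.005 in power), and say how participants without a six-month value are handled.
2. Keep the twelve-month Arm 1 versus Arm 2 comparison with the same method, described as earlier versus later start: by then Arm 2 has had classes, and continuation in Arm 1 is optional and paid. Report how many in each arm have a twelve-month TUG, since the remote procedures in I.c and III do not list it.
3. Keep paired or signed-rank tests for within-arm change only (Hypothesis 1, Arm 1 six versus twelve months, Arm 2 before versus after crossover), and label them so.
4. Report PAGEQ by arm at six months, not as change from baseline. Interpret it cautiously: it measures group cohesion, and Arm 2 may have no exercise group.
5. In II.a, restate power for the between-arm test with alpha, sidedness, 4.0 s as the single-visit SD, and the assumed correlation.

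The cost is some text in III.b and a revised power paragraph, with no new data or enrolment. The restated power falls below 90% for 3 s with 19 per arm if the correlation is under about 0.72 (ANCOVA) or 0.76 (test on change).
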